5.1.3.2 De-escalation of Dose Level

If Dose level 0 exceeds the MTD, lower doses will be studied as noted in the table above. If 1/3 patients have DLT at any dose level, the cohort will be expanded by 3 more patients. If ≥2/6 patients experience DLT, the MTD will be considered as being exceeded and the dose will be de-escalated to the next lower dose level and 3 new patients will be enrolled at that level. If none or only 1/6 patients experience DLT after dose de-escalation to the lower level, this dose level will be declared as the MTD, and will be utilized for the phase II component of the study.

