5.2. Phase II Component

5.2.1. Non-surgical Arm

In this component, patients will be randomized between three competing treatment arms: vorinostat + cRA, versus TMZ + cRA, versus vorinostat + cRA + TMZ using an adaptive randomization design (see 11.0 Statistical Section). The dosage of agents in each arm will be derived from the MTD of the combination determined in the phase I component of the study. The treatment schedule will be identical to that described above in the phase I component, with each course comprising 28 days (+ 3 days). Patients will continue treatment for at least one year from registration provided they experience neither tumor progression nor unacceptable toxicity (see 8.9). Treatment beyond this period is at the discretion of the treating physician after discussion with the patient. Vorinostat will continue to be provided free of charge to patients continuing treatment beyond 1 year.

Optional procedures: if available, brain tumor tissue from prior surgical procedures (original surgery, or definitive surgery, or the surgery closest to initiation of this clinical trial) will be obtained for determination of acetylation status and p21 levels (see 6.7). Blood samples for acetylation status of histones and p21 levels in

peripheral mononuclear cells will be also collected at baseline prior to treatment (6.6). Patients enrolled in arms 1 (vorinostat + cRA) and 3 (vorinostat + cRA + TMZ) will be evaluated with blood samples before and after treatment with vorinostat in day 1 of cycles 1 and 2 (see 7.10).

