5.4.2.3 Temozolomide

Dosing is based on adverse events (AEs) during the prior treatment cycle. If multiple AEs are seen, the dose administered should be based on the dose reduction required for the most severe grade of any single AE.

Dose Level	Dose mg/m ²	Remarks
- 2	75	Reduction if prior AE
-1	100	Reduction if prior AE
		Starting dose for cycle 1; increase to 150 mg/m^2 for cycle 2 and beyond if
0	125	non hematologic toxicity \leq grade 2

		and hematologic toxicity \leq grade 1
+1	150	Highest possible dose level

a) First Cycle: Temozolomide will be initiated at a dose of 125 mg/m²/day.

- b) Second Cycle: The dose of temozolomide will be determined according to: (1) treatment related non-hematologic AE during the preceding treatment cycle, as well as (2) the worst ANC and platelet counts. For patients at dose level 0, the dose may be increased to 150 mg/m2/dose for cycle 2 and beyond. If this dose is not tolerated, the dose may be reduced to the previous dose level.
- c) Delay: On day 1 of each cycle (within the prior 72 hours), ANC $\ge 1.5 \times 10^{9}$ /L, platelet count $\ge 100 \times 10^{9}$ /L and all grade 2, 3 or 4 nonhematologic AEs (except for alopecia, nausea, vomiting, weight change or DVT/PE – see section 5.3.3 – nonrelevant toxicities) must have resolved (to grade ≤ 1). For DVT/PE, the patient must have had adequate management of the event and be medically stable as determined by the treating physician prior to resuming treatment – this will be considered on a case by case basis after discussion between the treating physician and the study chair.

If AEs persists, treatment should be delayed by 1 week for up to 4 consecutive weeks. If, after 4 weeks of delay, all treatment related AEs have still not resolved (to grade \leq 1): then any further treatment with temozolomide should be stopped.

Dose Escalations and Reductions: If, during the first cycle, all hematologic AEs observed were \leq grade 1 and treatment related non-hematologic AEs observed were grade \leq 2 (except alopecia, lymphopenia, nausea, vomiting, weight gain and DVT/PE) then the temozolomide dose can be raised to 150 mg/m2/dose for subsequent cycles.

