Dose reductions: If any treatment related non-hematologic AE observed was grade > 2 (except alopecia, lymphopenia, nausea, vomiting, weight gain and DVT/PE) and/or if platelets < 50×10^{9} /L and/or ANC < 1×10^{9} /L, then the dose should be reduced by one dose level. Patients who require more than three dose reductions will have treatment stopped.

If any treatment-related non-hematologic AE observed was grade 4 (except alopecia, lymphopenia, nausea, vomiting, weight gain and DVT/PE) then temozolomide treatment should be stopped.

Subsequent cycles: Any dose reductions of temozolomide will be determined according to: (1) non-hematologic AE during the preceding

treatment cycle, as well as (2) the lowest ANC and platelets observed. No dose escalation should be attempted. The same dose reductions as for the second cycle should be applied. Important: If the dose was reduced or delayed for AEs, there will be no dose re-escalation in subsequent treatment cycles.

Summary of Dose Modifications or Discontinuation for Temozolomide-Related Adverse Events

Worst Treatment-Related Non-Hematologic AE (except for alopecia, nausea, and vomiting) During the Previous Cycles			
Grade	Dose Modification		
0-2	No dose modifications for non-hematologic AEs. Dose reductions based on ANC and platelet counts are applicable.		
3	Reduce by one dose level (except alopecia, lymphopenia, nausea, vomiting, weight gain and DVT/PE).		
4	Stop (except alopecia, lymphopenia, nausea, vomiting, weight gain and DVT/PE). Dose modifications based on ANC and platelet counts are not applicable.		

Worst Treatment-Related Hematologic AE During the Previous Cycle

Worst A	ΑE	Platelets		
		≥100 x 10 ⁹ /L	50 – 99 x 10 ⁹ /L	< 50 x 10 ⁹ /L
	≥ 1.5 x 10 ⁹ /L	Dose unchanged	Dose unchanged	Reduce by 1 dose level
ANC	≥1 & <1.5 x 10 ⁹ /L	Dose unchanged	Dose unchanged	Reduce by 1 dose level
	< 1 x 10 ⁹ /L	Reduce by 1 dose level	Reduce by 1 dose level	Reduce by 1 dose level

Note: A complete blood count must be performed on days 14 and 28 (\pm 72 hours) after the first daily dose of each treatment cycle.

Hematologic AE on Day 1 of Each Cycle (within the prior 72 hours before Day 1)			
AE	Delay		
ANC< 1.5 x 10 ⁹ /L and/or Platelet count < 100 x 10 ⁹ /L	Delay up to 4 weeks until all resolved. If unresolved after 4 weeks then stop. If resolved, dose delay/reductions based on non-hematologic AEs are applicable. If treatment has to be delayed for AEs, then no escalation is possible.		

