11.0 STATISTICAL CONSIDERATIONS

11.1 Phase I component

The phase I component will be a non randomized trial in which Arm 1 and Arm 2 will be opened simultaneously with consecutive patients enrolled alternately to each arm, and sequentially to each dose level. If the MTD is reached earlier in one arm, all subsequent patients will be enrolled to the other arm. Once the MTD for Arm 1 and Arm 2 is known, Arm 3 will begin accrual. A maximum of 54 patients will be enrolled in this component of the trial. The MTDs obtained in the Phase I component will be used as the Phase II dose in the next component of the trial.

11.1.1. Arm 1 of the phase I component was to assess the MTD of vorinostat in combination with a fixed dosage of cRA as shown in the table below. As noted above in section 5.1.1, the MTD of vorinostat in combination with cRA has been established in the current trial.

Level	Arm 1				
	Vorinostat cRA				
	(mg/day x 14 days) ((mg/m2/day x 21 days)				
0 (starting dose)	300	100			
1	400	100			
II	500	100			

11.1.2. Arm 2 of the phase I component was aimed at assessing the MTD of Carboplatin (CBT) in combination with a fixed dosage of cRA. With the change in the combination to temozolomide with isotretinoin, the MTD is already known; hence, a phase I trial of this arm will not be needed.

11.1.3. Arm 3 of the phase I component will assess the MTD vorinostat in combination with fixed doses of temozolomide + cRA. For temozolomide, the Phase II dose determined in Arm 2 will be used. The enrollment will proceed as outlined for Arm 1 (cohorts of 3 patients enrolled to each dose level), declaring MTD for Temozolomide in combination with vorinostat and cRA once DLT is noted.

Level	Arm 3		
	Vorinostat (mg/day x days 1-7 and 15-21)	cRA (mg/m2/day x 21 days)	Temozolomide (mg/m2/day on days 1-7 &15-21
-111	300	100	100
-11	300	100	125
-I	400	100	125
0 (starting dose)	400	100	150
I	500	100	150

- If the initial cohort of patients at starting dose level 0 do not experience DLT, the next cohort of patients will be treated by dose escalation to level I (with increase in the dose of vorinostat). If no patients experience DLT in this cohort, 3 more patients will be enrolled to expand this cohort to a total of 6 patient to confirm that MTD has been achieved. If no DLT is noted or if only 1/6 patients experience DLT after this expansion of level I, this dose level will be declared the MTD and hence the phase II dose.

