- If 2/6 patients have DLT after expansion of dose level I, dose level 0 will be declared as the MTD and hence the phase II dose.
- If Dose level 0 exceeds the MTD, lower doses will be studied as noted in the table above. If 1/3 patients have DLT at any dose level, the cohort will be expanded by 3 more patients. If ≥2/6 patients experience DLT, the MTD will be considered as being exceeded and the dose will be de-escalated to the next lower dose level and 3 new patients will be enrolled at that level. If none or only 1/6 patients experience DLT after dose de-escalation to the lower level, this dose level will be declared as the MTD, and will be utilized for the phase II component of the study.

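### The temozolomide schedule in Section 5.4.2.3 is not tied to the arm's MTD: it can exceed an Arm 3 MTD below level 0, starts below the stated Phase II dose otherwise, and the reduction limits disagree

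*Combined protocol and SAP*

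**What the plan says.** **Phase II dose.** Section 11.1 states "The MTDs obtained in the Phase I component will be used as the Phase II dose in the next component of the trial". Section 5.1.3.2 says of a tolerated lower Arm 3 level that "this dose level will be declared as the MTD, and will be utilized for the phase II component of the study". Section 5.2.1 says "The dosage of agents in each arm will be derived from the MTD of the combination". For Arm 2, Section 5.1.2 takes an externally established MTD of 150 mg/m2/day on days 1-7 and 15-21 and proposes that regimen for Phase II.

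**Temozolomide schedule.** Section 5.4.2.3 does not separate the arms. "Temozolomide will be initiated at a dose of 125" mg/m2/day is the cycle-1 instruction. If cycle-1 hematologic events were at most grade 1 and treatment-related non-hematologic events at most grade 2 (with listed exceptions), "then the temozolomide dose can be raised to 150 mg/m2/dose for subsequent cycles". The rise is barred after a delay: "If treatment has to be delayed for AEs, then no escalation is possible". The 150 row of the dose table is marked "Highest possible dose level", and that is the only ceiling. The section does not mention the arm's MTD. Section 5.4.2.1, by contrast, starts vorinostat at the MTD found for each arm.

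**Arm 3 levels.** The tables in Sections 5.1.3 and 11.1.3 put temozolomide at 150 for levels 0 and I, 125 for -I and -II, and 100 for -III. When a level fails, "the dose will be de-escalated to the next lower dose level and 3 new patients will be enrolled at that level". The text of 11.1.3 nevertheless describes temozolomide in Arm 3 as fixed, at the Arm 2 Phase II dose, which disagrees with the table beneath it. The label level 0 means 150 in those tables but 125 in Section 5.4.2.3.

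**Reductions.** Section 5.4.2.3 stops temozolomide after more than three reductions, and Section 8.9 also uses three. Section 10.0 item 5 ends treatment when more than two de-escalations of any drug are needed.

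**The concern.** A site treating a Phase II patient has two sets of dosing instructions and no statement of which governs. If Arm 3 de-escalates in Phase I, Section 5.4.2.3 can lead to a temozolomide dose above the declared MTD, including a drug combination that Phase I has just rejected. If Arm 3 does not de-escalate, and in Arm 2 in any case, the same section starts patients below the dose that the other sections call the Phase II dose.

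De-escalation is plausible. The plan provides three levels below the Arm 3 start. Section 2.6 says dose-dense temozolomide with vorinostat had not been explored. Section 2.11 reports that the carboplatin three-drug regimen was intolerable at its starting level and two lower levels. Carboplatin is a different drug, so this supports plausibility and gives no rate.

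The reduction limits matter for a different reason: they give two answers on whether a given patient stays on treatment.

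**Working it through.** There is no stated figure to reproduce. The check compares the schedule with each MTD that the plan allows.

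**1. Dose per cycle.** Days 1-7 and 15-21 make 14 temozolomide days, so dose per cycle = 14 x daily dose:
- 14 x 100 = 1,400 mg/m2
- 14 x 125 = 1,750 mg/m2
- 14 x 150 = 2,100 mg/m2

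**2. Schedule against MTD.** Percentages are relative to the MTD dose: 150/125 = 1.20, 125/100 = 1.25, 150/100 = 1.50, (150 - 125)/150 = 16.7%.

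| MTD | Vorinostat (mg) / temozolomide (mg/m2) | Per cycle at MTD (mg/m2) | Cycle 1 under 5.4.2.3 | Highest later dose under 5.4.2.3 |
|---|---|---|---|---|
| Arm 3, I | 500/150 | 2,100 | 1,750 (-16.7%) | 2,100 (equal) |
| Arm 3, 0 | 400/150 | 2,100 | 1,750 (-16.7%) | 2,100 (equal) |
| Arm 3, -I | 400/125 | 1,750 | 1,750 (equal) | 2,100 (+20%) |
| Arm 3, -II | 300/125 | 1,750 | 1,750 (equal) | 2,100 (+20%) |
| Arm 3, -III | 300/100 | 1,400 | 1,750 (+25%) | 2,100 (+50%) |
| Arm 2 | none/150 | 2,100 | 1,750 (-16.7%) | 2,100 (equal) |

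**3. Which combinations result.** Vorinostat starts at the arm's MTD (Section 5.4.2.1).
- MTD -I with the rise gives 400/150, which is rejected level 0.
- MTD -II with the rise gives 300/150, which is not in the table.
- MTD -III in cycle 1 gives 300/125, which is rejected level -II.

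**4. Chance that level 0 is rejected.** The documents give no DLT rate, so the true rate p at level 0 is an assumption. Rejection is read as two or more DLTs in the first three patients, or one in three followed by at least two in six. Level 0 survives with 0/3, or with 1/3 then 0/3, so

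P(reject) = 1 - (1-p)^3 - 3p(1-p)^5

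- p = 0.10: 1 - 0.729 - 0.177 = 0.094
- p = 0.20: 1 - 0.512 - 0.197 = 0.291
- p = 1/3: 1 - 0.296 - 0.132 = 0.572
- p = 0.50: 1 - 0.125 - 0.047 = 0.828

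These are upper bounds on the chance of the above-MTD case, because levels -I to -III could also fail and leave no MTD. As an illustration, suppose all four levels share the same p and the same rejection rule. With q = P(reject), the chance of an MTD at -I to -III is q - q^4:
- p = 1/3: 0.572 - 0.107 = 0.465
- p = 0.50: 0.828 - 0.470 = 0.358

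DLT rates that fall with dose would narrow the gap to the bound.

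**5. Reductions.** The dose steps in 5.4.2.3 are 150, 125, 100 and 75, so there are three steps down from 150, two from 125 and one from 100. Only a patient raised to 150 has a dose defined for a third reduction (100 to 75). At that point 5.4.2.3 and 8.9 continue treatment and 10.0 item 5 stops it.

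**The case against.** The strongest reply is that Section 5.4.2.3 sits under dose modifications, while Sections 5.1.3.2, 5.2.1 and 11.1 all derive the Phase II dose from the MTD, so the missing link is more likely an omission than an instruction to exceed the MTD. That is a fair reading of intent. It does not settle the text: no section is given precedence, and 5.4.2.3 is the more specific passage and the one a site would consult for a dose.

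There are also safeguards. The rise is optional, depends on a well-tolerated cycle 1, and is barred after a delay. Temozolomide is reduced first for thrombocytopenia or anemia in Arm 3. DLTs are reviewed after every 10 patients per arm (Sections 9.1 and 11.2). Arm 3 Phase I must finish before its Phase II dose is known, and Section 2.11 shows that the investigators held accrual and amended the plan when the carboplatin regimen failed. These reduce the risk, but none is a cap at the MTD, and the cycle-1 toxicity gate cannot act on the cycle-1 excess at level -III.

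On the reduction count, 5.4.2.3 describes stepping back from 150 as a return to the previous level. If that step were not counted, two further reductions below 125 would fit Section 10.0. The plan does not say so.

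A reader might infer that Arm 3 patients will be overdosed, or that the 9% to 83% range is the chance of it. The documents support neither. The Arm 3 MTD is not reported, and the range concerns rejection of level 0 under assumed DLT rates.

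**Conclusion.** The point holds as an internal inconsistency that should be fixed. The temozolomide schedule conflicts with the Phase II dose rule at every MTD the plan allows, in a direction that depends on the MTD.

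The above-MTD part is conditional on an Arm 3 MTD below level 0: 20% above (350 mg/m2 per cycle) from cycle 2 at -I or -II if the rise is taken, and at -III 25% above (350 mg/m2) in cycle 1 and up to 50% above (700 mg/m2) later. In Arm 2, and in Arm 3 at level 0 or I, the MTD is never exceeded; cycle 1 is 16.7% (350 mg/m2) below the stated dose, and 150 is reached only if the optional rise is taken.

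The reduction-count conflict does not depend on the Arm 3 MTD, but it is minor: it affects only patients raised to 150 who need a third reduction.

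These are dose figures. They do not estimate added toxicity, and they bear on no sample size or operating characteristic.

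**What to change.** - **5.4.2.3:** add that neither the temozolomide starting dose nor any escalation may exceed the arm's MTD dose. For Arm 3: MTD -III, 100 with no rise; MTD -I or -II, 125 with no rise; MTD 0 or I, 125 with optional 150.
- **5.1.2, 5.2.1 and 11.1:** state that 125 with an optional rise to 150 is the intended Phase II regimen for Arm 2 and for Arm 3 at MTD 0 or I. If the sponsor intends a 150 start instead, say that and change 5.4.2.3 to match.
- **11.1.3:** reconcile the fixed-dose wording for temozolomide with the dose table, and avoid using level 0 for two different doses.
- **9.1 and 11.2:** define temozolomide level -1 in the safety rule as one step below the arm's starting dose (125 to 100, or 100 to 75). Otherwise a start capped at 100 would equal the present -1 level and the rule would lower nothing.
- **5.4.2.3, 8.9 and 10.0:** state one temozolomide reduction count, noting that the table ends at 75 (three steps from 150, two from 125, one from 100).

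The cost is a wording amendment, best made before Phase II opens, with no added patients or procedures. Arm 2 dosing changes only if the sponsor chooses the 150 start.

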5.4. Dose modifications

5.4.1 Subsequent Cycles

Treatment cycles will be repeated every 28 days (+ 2 days) from day 1 provided that the tumor has not progressed and the patient has recovered from treatment-related adverse events associated with a prior course. Recovery has occurred once all of the following conditions have been met:

a) ANC >1500/mL;

b) Platelet Count >100,000/mL;

c) All drug-associated non-hematological toxicities have recovered to either Grade 0 or 1(except for deep venous thrombosis as below).

If recovery has not occurred by **Day 28** (+ 3 days), the subsequent cycle will be delayed until these criteria have been met. If the patient has not recovered within 4 weeks of rest, he/she will be taken off study. However, if the patient develops a lower extremity deep venous thrombosis and requires anticoagulation or intervention (grade 3 toxicity), treatment may be restarted after a 2 week rest period if the patient

is stably anticoagulated and is judged medically stable to begin chemotherapy, in the opinion of the treating physician. (Please note: DVT is graded in the CTC version 3.0 as grade 1= not defined, grade 2= DVT without need for anticoagulation or intervention, grade 3= DVT needing anticoagulation or intervention).

The administration of vorinostat, isotretinoin and temozolomide in subsequent cycles will continue at the same doses without interruption as long as there is no tumor recurrence or progression and toxicity is acceptable.

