5.4.2.1 Vorinostat

Vorinostat will be administered from day 1 -14 in arm 1 and on days 1-7 and 15-21 in arm 3. Treatment will be initiated at the MTD dose determined in the phase I component of the trial for each arm. This dose will be maintained as long as there are no toxicities \geq grade 3. For grade 3 or greater toxicities, treatment will be withheld and the patients will be monitored until toxicities resolve to < grade 2 (except for deep venous thrombosis as noted in section 5.3). Subsequent treatment will be at one dose level lower than the one that caused the toxicity. If there is grade 3 or greater non-hematologic toxicity, a minimum of 2-week rest period will be required. Subsequently, patients will restart treatment at one dose level less than the one that resulted in the toxicity as indicated below.

Dose adjustments for the subsequent cycles: dose will be one level below the dose that produced toxicity of grade 3 or greater per dose schedule changes indicated below. If grade 3 or 4 toxicity recurs, patients will again discontinue the vorinostat until toxicity returns to grade 1 or less. The estimated dose levels below are shown for various MTD that may be determined in the phase I study.

In case of thrombocytopenia or anemia in Arm 3 (vorinostat + cRA + TMZ), TMZ will be dose-reduced first, and then vorinostat on an alternating basis for each time a dose reduction becomes necessary.

Dose Level:	-2	-1	0
Drug			MTD Phase I
Vorinostat	N/A	200 mg once daily	300 mg once daily
	200 mg once daily	300 mg once daily	400 mg once daily

300 mg once daily	400 mg once daily	500 mg once daily

Only 2 dose reductions of vorinostat are permitted as above. If the patient experiences grade 3 or greater toxicity after 2 dose reductions, he/she will be taken off study. If starting dose is 300 mg once daily, only 1 dose reduction of vorinostat is allowed.

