10.0 CRITERIA FOR DISCONTINUATION OF TREATMENT

- 1. Progressive disease as defined above after one cycle of treatment. (Section 8.2.5).
- 2. The development of unacceptable toxicity.
- 3. Patient refusal.
- 4. Non-compliance or inability to comply with protocol requirements by patient
- 5. Treatment related adverse events not resolved within a 4 weeks rest period or requiring more than two dose de-escalations of any drug whichever is earlier.

Patients may remain on treatment as long as disease progression is not observed and the patient is not experiencing unacceptable toxicity (see 8.9). Although therapy is planned for one year, the patient may remain on treatment beyond this time if both the patient and physician agree that further therapy is in the patient's best interests.

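### In Arms 2 and 3, Sections 5.4.1, 5.4.2.3, 8.9 and 10 give conflicting rules for delaying and ending treatment, and the rule applied can decide whether PFS is still assessed

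*Combined protocol and SAP*

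**What the plan says.** **Toxicity not recovered after 4 weeks**
- Section 5.4.1, which covers all three drugs: "If the patient has not recovered within 4 weeks of rest, he/she will be taken off study".
- Section 10, item 5, in the list of reasons to discontinue treatment: "Treatment related adverse events not resolved within a 4 weeks rest period".
- Section 5.4.2.3, after 4 weeks of delay: "then any further treatment with temozolomide should be stopped". Vorinostat and isotretinoin (cRA) are not mentioned. The delay tables in the same section say only to stop, without naming what stops.

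**Conditions for starting the next cycle**
- Section 5.4.1(c): "All drug-associated non-hematological toxicities have recovered to either Grade 0 or 1(except for deep venous thrombosis as below".
- Section 5.4.2.3 also exempts alopecia, nausea, vomiting, weight change and pulmonary embolism (PE).

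**Limit on dose reductions**
- Section 10, item 5: "Treatment related adverse events not resolved within a 4 weeks rest period or requiring more than two dose de-escalations of any drug".
- Section 5.4.2.3 stops treatment only when more than three temozolomide reductions are needed. Section 8.9 likewise defines unacceptable toxicity by reference to three temozolomide reductions and two of the other drugs (one if vorinostat starts at 300 mg).

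**Grade 4 non-hematologic event**
- Section 5.4.2.3: "then temozolomide treatment should be stopped".
- Section 5.4.2.1, for vorinostat after grade 3 or greater: "Subsequent treatment will be at one dose level lower than the one that caused the toxicity". Section 5.4.2.2 has the equivalent rule for cRA.

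**The concern.** The general sections and the temozolomide section were evidently written separately, and in Arms 2 and 3 both apply. Two investigators could handle the same patient differently, each with a section of the protocol in support.

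This reaches the primary endpoint. Section 7.3 schedules MRI after every two cycles of treatment. Once treatment on protocol is completed, Section 7.8 provides for overall survival follow-up only. A patient judged off treatment without progression may therefore leave scheduled scanning, while one judged still on treatment is scanned. PFS also drives adaptive allocation, arm dropping and arm selection (Section 11.2), so the handling of such patients enters decisions made during the trial as well as the final estimate.

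**Working it through.** The point is a comparison of rules; the only arithmetic is counting dose steps and days.

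**1. Do the rules reach the same patient?** Section 5.4.1 closes by naming vorinostat, isotretinoin and temozolomide, so it covers Arms 2 and 3 as well as Arm 1. Its recovery thresholds match those of 5.4.2.3: ANC 1,500 and platelets 100,000 against 1.5 and 100 × 10⁹/L, with non-hematologic toxicity at grade 1 or less. This reads the 5.4.1 counts as per mm³, the unit used in Section 4.10.

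**2. Arm 3 patient, platelets still below threshold after 4 weeks**

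| Text | What ends |
|---|---|
| 5.4.1 | The patient is off study (term not defined) |
| Section 10, item 5 | Treatment |
| 5.4.2.3, Delay | Temozolomide; other drugs not mentioned |
| 5.4.2.3, tables | Object not named |

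No text ranks these rules.

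**3. Arm 2 or 3 patient, persistent drug-related grade 2 nausea.** Under 5.4.1(c) recovery has not occurred, so the cycle is delayed; after 4 weeks the patient is off study. Under 5.4.2.3 nausea is exempt and there is no delay. PE also differs: the exception in 5.4.1 is for lower-extremity deep venous thrombosis, while 5.4.2.3 lets a stable patient resume after PE, case by case.

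Section 5.3 settles part of this. It rules out modifying study agents for weight gain and does not grade alopecia. It does not exempt nausea or vomiting, and its sentence on resuming therapy names deep vein thrombosis only. Weight loss remains open: the Delay text of 5.4.2.3 exempts weight change, its tables only weight gain.

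**4. Third temozolomide reduction.** The levels in 5.4.2.3 are 150, 125, 100 and 75 mg/m². From 150 there are three steps down (150→125→100→75); from 125 there are two. A patient who has reached 150 and needs a third reduction is discontinued under Section 10 (3 > 2). Under 5.4.2.3 the same patient is reduced to the lowest level (3 is not more than 3), and 8.9 is not met until grade 3 or greater toxicity follows that third reduction. A patient never above 125 has no third lower level in the table.

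**5. Temozolomide stopped alone.** After a grade 4 non-hematologic event, 5.4.2.3 stops temozolomide, while 5.4.2.1 and 5.4.2.2 withhold and then reduce the other drugs. Section 5.4.2 manages toxicity by causative agent, so these rules are compatible. What is missing is whether the remaining drugs (vorinostat + cRA in Arm 3, cRA alone in Arm 2) count as protocol treatment. Neither 8.9 nor Section 10 says.

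**6. The 4-week clock.** The start of the rest period is undefined. Assuming rest runs from the last dose on day 21, it ends on day 21 + 28 = 49. Delay counted from the due date, day 28, ends on day 28 + 28 = 56. The gap is 7 days. The conclusion does not depend on this assumption.

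**The case against.** **The best defence.** Taking a patient off study also stops temozolomide, so applying the strictest text formally satisfies all three rules at 4 weeks. The protocol also seems to use off study for events that elsewhere merely end treatment: grade 3 or greater toxicity after two reductions is off study in 5.4.2.1 and 5.4.2.2, and is unacceptable toxicity, hence a reason to end treatment, in 8.9 and Section 10. On that view there are two outcomes, and 5.4.2.3 is silent about the other drugs rather than contrary. This has force, but nothing says the strictest text governs. If it did, the exemptions for nausea, vomiting and PE in 5.4.2.3 would have no effect. It also does not resolve the third reduction, where one text discontinues and the other reduces.

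**Other safeguards.** Intent-to-treat (11.2) fixes the assigned arm but does not secure continued assessment or state how such patients are censored. MRI at any clinically indicated time (7.3) is not a schedule. The group in 12.3 settles disputes over response or toxicity, not which section applies. Missing scans after treatment are a problem in their own right; reconciling the stopping rules alone would not cure that.

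**Stronger readings that a reader might infer, and that the documents do not support:**
- *That a grade 4 event as such ends participation under one rule and all treatment under another.* No rule does either for a first grade 4 event that resolves. The off-study and unacceptable-toxicity rules apply only after the permitted reductions.
- *That Arm 3 patients drift onto the Arm 1 regimen.* Continuation of vorinostat + cRA is an inference from silence, and Arm 3 gives vorinostat on days 1-7 and 15-21, not days 1-14.
- *That off study ends all participation.* The term is undefined, and 7.8 still plans survival follow-up.
- *That different sites will diverge.* Section 2.11 describes a modification of a single-institution trial.
- *That the temozolomide arms are treated more leniently throughout.* 5.4.2.3 is looser on exemptions but stricter on grade 4.
- *That the frequency can be read from the adverse-event table.* Vorinostat-related nausea is 55.7% at all grades and 5.6% at grade 3-5. Neither is the rate of grade 2 or higher nausea persisting through 4 weeks of delay.

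**Conclusion.** The concern holds for three rules in Arms 2 and 3: the consequence of non-recovery at 4 weeks, the exemptions at the next-cycle check, and the temozolomide reduction limit. The status of a patient who stops temozolomide alone is a gap, not a further contradiction.

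The number of patients affected cannot be computed, since the documents give no rate for any of these triggers, and an assumed percentage would have no anchor. A few patients could still matter: the lower 2.5% limit for patients per arm in the simulations is 10 to 14. The consequence for PFS rests on two readings: that MRI scheduled by cycle stops when treatment stops, and that 7.8 is the whole of the follow-up after treatment. Both are what the text says, though practice may be more generous. The point should be corrected; it does not alter the sample size or the decision thresholds.

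**What to change.** Reconcile 5.4.1, 5.4.2.1 to 5.4.2.3, 8.9 and Section 10 into one table for all arms:
- For each trigger, state whether one drug, all study drugs or study participation ends, and define off study.
- Use one list of exempt toxicities for the next-cycle check, with nausea, vomiting, weight change and PE each addressed.
- Give one reduction limit per drug and one starting point for the 4-week period.
- State whether a patient who stops one component remains on protocol treatment.

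State also that a patient who stops any component, or all treatment, without progression stays in the assigned arm with MRI on the same schedule. Two 28-day cycles make 56 days, so this can be written as a calendar interval. Record the stop date and reason separately for each drug. Which clinical rule applies to each trigger is for the sponsor to decide.

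Cost: one amendment table and a per-drug stop field, with no additional patients. Patients who stop all treatment without progression would continue scheduled MRI, which the current text does not provide for; their number cannot be estimated from the documents.
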